9. ANALYSIS PLAN

9.1 Primary Analyses

Our primary analyses will use an intent-to-treat (ITT) approach using repeated measures logistic regression to compare the overall effect of the intervention on patient adherence. We will also explore potential differences in secondary outcomes across arms. Baseline clinical and survey data will be used

to assess potential differences in treatment groups (i.e., socio-demographics and clinical risk factors) using parametric or nonparametric tests as appropriate. Data quality, normality, and other assumptions will be assessed prior to analysis. Using repeated measures logistic regression fitted using generalized estimating equations (GEE), we will compare the proportion of adherent days between Penny and usual care. Data will be treated as binary outcome (0/1) over the study period. Models will contain a predictor term for treatment arm, will be adjusted for time (discrete week), and will contain subject specific random effects and fixed effects for site. Patients will be categorized as adherent (outcome=1) across the study period if the total percentage of adherent days is $\geq 95\%$ similar to previous studies⁷; other percentages (80%, 90%, 100%) will be explored in sensitivity analyses. Persistence will be treated as repeated measure survival data and will be summarized as median survival time using Kaplan-Meier methods. We will also generate summary statistics (including mean adherence rate) to help describe the study population and inform the design of further studies.

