Outcomes	
 • Primary Outcome: Adherence (measured using MEMS caps) defined by the overall proportion of adherent days and classified dichotomously as adherent if total proportion of days is ≥95%

	
 • Secondary Outcomes: Persistence defined as the number of consecutive days on the regimen and conversely gaps in overall treatment • Exploratory Outcomes: Patient-reported outcomes including health-related quality of life (HRQOL), symptom burden, patient satisfaction, financial toxicity, social and behavioral determinants of health (SBDH), medication self-efficacy, and health literacy
Primary Analysis	Intent-to-treat (ITT) analyses using repeated measures logistic regression to compare the overall effect of the intervention on patient adherence
Secondary Analyses	Baseline survey and clinical data will be used to explore potential mediators and moderators of treatment effects. Standard mediation analysis will be used to explore separately whether symptom management or self-efficacy mediates treatment effects. Multivariable regression analysis with intervention, moderator, and interaction terms will be used to assess effect modification by patient characteristics based on significance of the interaction term.
Study Oversight	Trial oversight will be conducted by the University of Pennsylvania Institutional Review Board. Safety will be monitored on an ongoing basis by the co-PIs, study team, and institutional experts at Penn Medicine not directly involved in the study.

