4.2 Primary Outcome

The primary outcome is adherence to prescribed oral targeted therapy across the 12-week trial period. Adherence is defined by the overall proportion of adherent days and classified dichotomously as adherent if total proportion of days is $\geq 95\%$. Longitudinal adherence outcomes for all participants will be captured using microelectronic monitoring system (MEMS) caps, surveys, and electronic medical record (EMR) data.

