8.3 Measures

Adherence (Primary Outcome). For each participant, adherence will be calculated based on the overall proportion of adherent days (defined dichotomously based on whether a patient took all prescribed doses for the day within 2 hours of recommended time). Participants who are 95% adherent or above will be classified as adherent (1) and those below will be considered not adherence (0). For therapies that have more than one dose per day, we will also calculate the proportion of doses taken among all prescribed doses. Additionally, we will evaluate persistence as a secondary adherence outcome (defined as the number of consecutive days on the regimen and conversely gaps in overall treatment) to assess how Penny may impact different dimensions of adherence. Adherence will also be assessed via self-report (using a validated visual analog rating scale)^{34,35} and prescription refill orders from the EMR to assess accuracy of self-report and provide contingency measures to support potential, yet unlikely, failures in MEMS caps.³⁶

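### The primary outcome and its power are one ≥95% status per patient, but the primary model in 9.1 is a repeated-measures GEE on adherent days whose response and row unit are never stated and whose terms fit neither reading

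*Combined protocol and SAP*

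**What the plan says.** **Outcome.** The Summary, 4.2 and 8.3 agree on one value per patient. Section 4.2: "Adherence is defined by the overall proportion of adherent days and classified dichotomously as adherent if total proportion of days is" at least 95%. Section 8.3: "Participants who are 95% adherent or above will be classified as adherent (1) and those below will be considered not adherence (0". Section 8.3 also scores each day as 0/1, as the building block of that status.

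**Power.** Section 5.5 assumes 65.5% adherence in controls and claims 80% power for a 20.9-point difference by Fisher's exact test. It allows for 15% loss, which leaves 72 per arm.

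**Model.** The Summary's Primary Analysis row gives "Intent-to-treat (ITT) analyses using repeated measures logistic regression to compare the overall effect of the intervention on patient adherence". Section 9.1 says "Using repeated measures logistic regression fitted using generalized estimating equations (GEE), we will compare the proportion of adherent days between Penny and usual care", and then "Models will contain a predictor term for treatment arm, will be adjusted for time (discrete week), and will contain subject specific random effects", plus site as a fixed effect. The same paragraph returns to the patient: "Patients will be categorized as adherent (outcome=1) across the study period if the total percentage of adherent days is" at least 95%, and "other percentages (80%, 90%, 100%) will be explored in sensitivity analyses". It says the data are handled as 0/1 over the study, but does not name the unit that carries the 0 or 1. The mediation models in 9.2 use daily adherence.

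**The concern.** A status fixed over the whole study gives one row per patient, with nothing repeated and no week to adjust for. A repeated-measures model with a week term needs day or week rows, and those carry a different outcome from the one defined and powered. The model sentence also joins two methods: GEE gives a marginal odds ratio, whereas subject random effects belong to a mixed model with a conditional odds ratio.

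An analyst following 9.1 could therefore report any of three quantities as the primary result: a patient-level comparison, a marginal daily odds ratio or a conditional daily odds ratio. These can differ on statistical significance. The trial is open label and the PIs are unblinded (6.3), although the statistician and analyst are to be blinded, so the choice should be fixed in writing before analysis.

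**Working it through.** **1. Reproduce the plan's power.** Inputs from 5.5: control 65.5%; intervention 65.5% + 20.9 = 86.4%; 170 × 0.85 = 144.5, hence 72 per arm. Alpha and sidedness are not stated; 0.05 two-sided is assumed. Power is the sum, over all pairs (x, y) of adherent counts, of Bin(x; 72, 0.655) × Bin(y; 72, 0.864) wherever Fisher's p ≤ 0.05.

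- Fisher, 72 per arm: 0.8003. The smallest detectable difference is 20.9 points, so the plan's figure reproduces.
- Fisher, 85 per arm at the same rates: 0.871. The 80% therefore belongs to the 144 evaluable patients and not to the full 170.
- Unadjusted logistic Wald test, 72 per arm: 0.845.

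This calculation needs one binary value per patient. Section 5.5 does not say that 65.5% is a ≥95% rate. That is inferred because 5.5 and the ≥95% rule in 9.1 cite the same reference (7).

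**2. Try each row unit against the model in 9.1.**

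| | Rows are patients | Rows are days |
|---|---|---|
| Response | ≥95% status | day adherent or not |
| Week term, within-patient correlation | not estimable | estimable |
| Defined outcome tested? | yes | no |
| Does the 80% apply? | yes, by Fisher | no |
| Subject random effects in GEE? | no | no |

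Neither column makes the paragraph coherent.

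**3. How the two outcomes separate.** With full follow-up of 12 × 7 = 84 days, 0.95 × 84 = 79.8, so 80 days are needed (80/84 = 95.2%; 79/84 = 94.0%). Moving from 42 to 79 days adds 37/84 = 44 points of adherent days with no change in status. Moving from 79 to 80 adds 1.2 points and changes status. The 80-day threshold holds only for full follow-up, because 5.3 ends observation at discontinuation if that comes sooner. At 28 days, 27 are needed; at 56 days, 54.

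**4. Illustration of size.** The documents give no within-patient dispersion, so it is assumed. Each patient's days are beta-binomial over 84 days, everyone is fully followed, there are 72 per arm, and each arm is calibrated so that 65.5% or 86.4% reach 80 days. The day-level test is the difference in log-odds of the mean daily proportion with a cluster-robust SE (20,000 trials per row). With concentration s, the within-patient correlation is 1/(s + 1).

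| s | Correlation | Day-level OR | Day-level power | Differs from Fisher on significance |
|---|---|---|---|---|
| 2 | 0.333 | 2.94 | 0.732 | 0.207 |
| 5 | 0.167 | 2.76 | 0.810 | 0.174 |
| 10 | 0.091 | 2.55 | 0.891 | 0.152 |
| 20 | 0.048 | 2.27 | 0.949 | 0.159 |
| 50 | 0.020 | 1.89 | 0.976 | 0.181 |

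The patient-level odds ratio is (0.864/0.136)/(0.655/0.345) = 3.35 throughout. Estimates point in opposite directions in at most 0.4% of trials. For comparison, Fisher and logistic Wald on the same patient-level data differ on significance in 4.5%. Set against logistic Wald instead of Fisher, the day-level test differs in about 12–20% (6,000 trials).

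**5. Marginal against conditional.** Under a normal random intercept with assumed SD 0.5 to 3, calibrated the same way, the marginal daily odds ratio runs from 1.64 to 3.46 and the conditional one from 1.65 to 8.39. How far GEE and a mixed model part depends on the SD, which the documents do not give.

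**The case against.** Section 9.1 never says that rows are days. It speaks of a 0/1 outcome over the study period and codes the patient status as outcome = 1, so the status may well be the intended response. Outcome and power would then agree, and the fault would be surplus repeated-measures terms. The random-effects phrase may be loose wording for within-patient correlation. This is also a pilot, and the illustration rests on assumed dispersion and complete follow-up.

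Much of this stands. It rules out the flat statement that the plan analyses a different outcome from the one it defines; that is true only on day rows. It does not rescue the paragraph, because on patient rows the stated week term and repeated-measures structure cannot be fitted.

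A reader might also infer three stronger things that the documents do not support:

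- That the sample size is wrong. It reproduces; it simply does not cover a day-level model.
- That a day-level analysis would lose power. In the illustration, power is below 80% only at the strongest correlation shown, and the direction of effect is almost never reversed.
- That power falls because lost patients count as non-adherent. No section prescribes such scoring; the handling of missing data is a separate question.

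**Conclusion.** The concern holds in this form: the outcome and its power are per patient, and the primary model in 9.1 names neither its response nor its row unit and carries terms that fit no single reading. Row 2 of the working rests on the text alone. The 80.0% assumes a two-sided 0.05 test and that 65.5% is a ≥95% rate. The sizes (day-level power of about 73–98%, and a different significance conclusion from Fisher's in about 15–21% of trials) are illustrative and depend on the assumed dispersion and 84 days for every patient. Because this is the headline analysis, it must be settled before analysis.

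**What to change.** In 9.1 and the Summary's Primary Analysis row:

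- Make the primary analysis one record per patient, with the ≥95% status as response, by logistic regression on arm and site (site adjustment is already planned).
- Report the difference in proportions with a 95% CI, obtained by standardisation from that model, or unadjusted and labelled as such.
- Remove the week term and the random effects from the primary model.
- Keep the daily-row GEE (arm, week, site, a stated working correlation, robust SE, no random effects) as a named secondary analysis, and say that the mediation models in 9.2 use this daily outcome.

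In 5.5, state that the 80% applies to the ≥95% status in 72 evaluable patients per arm by Fisher's exact test, and not to the full sample. Add that it is a conservative basis for the logistic analysis (unadjusted Wald 84.5%).

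If the sponsor prefers daily adherence as primary, the outcome definition and the power calculation must both be rewritten to match, with a stated mean daily adherence and within-patient correlation.

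The cost is rewording; no new data are needed. The downside is that any extra precision of the day-level model is not used for the headline test.

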7.2 Consent and Enrollment

Aim 1: Consent Discussion (Trial participants): If a patient expresses interest in participating following the study introduction, the patient will be contacted by phone to have a consent discussion in accordance with Penn Medicine remote consent procedures. During the consent discussion, we will discuss the voluntary nature of the study, risks and benefits of participation, randomization, and answer any questions that the participant may have. We will discuss the potential accessibility of patients' health information by a third party, Memora Health, for withdrawal of specific data points necessary for the development and programming of "Penny" (name, drug type, prescription, contact information). We will ask patients to verbally confirm willingness to participate or decline participation.

Aim 1: Documentation of Consent (Trial participants): For those participants who verbally confirm willingness to participate during the consent discussion, we will use REDCap to document consent as recommended by Penn Medicine remote consent procedures. The individualize REDCap link will include the full informed consent form and ask participants to document consent and understanding prior to proceeding to the baseline survey. We will also mail and/or email participants a copy of the informed consent form (included in this protocol) that will include information on how to contact the research team via email or phone if they have study related questions, concerns or choose to withdrawal from the study at any time. Only participants who document consent and complete the baseline survey will be randomized and included in this study.

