8.2 Assessment Procedures

MEMS Caps. Adherence data will be assessed via MEMS caps, which capture a date and time stamp each time the pill bottle is opened. MEMS caps are considered the gold standard of objective adherence measurement over other methods of adherence monitoring,^{31,32} and have been used successfully in previous studies of oral anticancer agents.^{5,25} MEMS data will be scanned to a secure web portal by research staff at the time of clinic appointments. All participants will receive MEMS cap(s) regardless of study assignment. Participants will be instructed to use this system for storage throughout the study, and to log any bottle openings for purposes other than pill ingestion (e.g., to check remaining supply) in a daily journal. After patients complete the baseline survey, a study team member will mail the MEMS Caps directly to the patients with instructions on how to install the MEMS cap. Patients will be contacted by phone approximately 7-10 days after the MEMS cap is mailed to them to confirm receipt and answer any questions. Patients will be instructed to begin using the MEMS cap the day immediately following the phone call as this will be their study start date.

Online Surveys. Trial participants (Aim 1) will be asked to complete online surveys at three timepoints: baseline assessment (T0) will occur at time of enrollment, followed by mid-point assessment approximately 6 weeks later (T1), and final assessment occurring within 2 weeks of trial completion (T2). Data will be captured via REDCap, a secure, web-based application for collecting and managing survey data³³. For REDCap data, patients will receive individualized links to each survey and will be contacted up to three times by email, text message, and/or phone to complete each survey. To increase data completion and study retention incremental compensation will be provided to patients. Specific measures to be assessed in the survey are described below.

Medical Record Data: Medical record data from enrolled patients will be abstracted across the study period to evaluate diagnostic and treatment changes, clinical characteristics, and healthcare utilization. We will also use medical record data to identify and recruit potentially eligible patients as outline in the HIPAA waiver.

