9.2 Exploratory Analyses

In exploratory analyses, we will apply standard mediation analysis to explore separately whether symptom management or self-efficacy mediates the relationship between arm assignment and adherence. We will conduct multivariable regression to explore the following: (1) if arm assignment has an effect on symptom management or self-efficacy, (2) if either of these intermediate outcomes has an effect on daily adherence; (3) if arm assignment has an effect on daily adherence, or (4) if the effect of arm assignment on daily adherence shifts when either of these intermediate outcomes is added to the model. Rejecting the null for all four hypotheses will be necessary to support either symptom management or medication self-efficacy as a mediator. We will use a modified Sobel test for significance testing. Additionally, we will explore for potential effect modification across different patient subgroups based on patient demographics, health literacy, social determinants of health, clinical characteristics, and other factors. We will fit multivariable regression models with intervention, moderator, and interaction terms to assess potential effect modification based on significance of the interaction term. As planned analysis, we will also explore mortality differences between study arms at 6- and 12-month follow-up using data collected passively from the EHR (as outlined in the consent form).

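### The primary model adjusts for no baseline survey or prognostic covariate, although every randomised patient must complete that survey first: a cheap improvement of unknown size

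*Combined protocol and SAP*

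**What the plan says.** Section 9.1 (Primary Analyses) describes repeated measures logistic regression and lists its terms: "Models will contain a predictor term for treatment arm, will be adjusted for time (discrete week), and will contain subject specific random effects", together with "fixed effects for site". No survey score or clinical risk factor is among them. Of the three stratification factors in section 6.2 (medication status, drug class, hospital), only hospital appears, if site means hospital.

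The same section uses baseline clinical and survey data "to assess potential differences in treatment groups (i.e., socio-demographics and clinical risk factors) using parametric or nonparametric tests as appropriate". It does not say what follows from a significant result.

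Baseline data have further uses elsewhere. The Protocol Summary (section 1) states: "Baseline survey and clinical data will be used to explore potential mediators and moderators of treatment effects". Section 9.2 adds: "We will fit multivariable regression models with intervention, moderator, and interaction terms to assess potential effect modification". These analyses are labelled secondary in the summary and exploratory in 9.2.

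On timing, section 8.2 says that "baseline assessment (T0) will occur at time of enrollment", and section 7.2 says: "Only participants who document consent and complete the baseline survey will be randomized and included in this study". Section 6.2 has patients learn their arm after the survey. MEMS caps are mailed only after the survey (8.2).

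On content, section 8.3 names SEAMS for medication self-efficacy and ESAS for symptom burden. It also says: "Adherence will also be assessed via self-report (using a validated visual analog rating scale". It gives no time point for any of the three, and says that outcomes are collected at varying time points to limit burden.

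**The concern.** A covariate that is measured before assignment and predicts the outcome can make the estimated arm effect more precise without extra patients. The trial has a nearly ideal source: a survey that every randomised patient has completed before learning the arm. Missing values should be limited to skipped items, and no value can be affected by treatment. Section 9.1 does not use it for the primary estimate.

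The between-arm tests do not fill that role. Under randomisation any baseline difference is due to chance, so the null hypothesis is true by design, and a p-value does not show whether an imbalance matters for the outcome. With no consequence laid down, a small p-value is either ignored or prompts adjustment chosen after the fact. The latter is undesirable in an open-label trial whose PIs are unblinded (6.3), even though the statistician is blinded.

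At stake are some precision and a pre-specified answer to chance imbalance. Validity is not at stake.

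**Working it through.** **Inputs.** From section 5.5: control rate 65.5%; difference 20.9 points, so 65.5 + 20.9 = 86.4% with Penny; 72 per arm after 15% loss; Fisher's exact test; 80% power. Alpha is not stated and is assumed to be 0.05 two-sided. The documents give no correlation between any baseline score and MEMS adherence, so covariate strength is assumed over a range.

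**1. The plan's own figure.** 170 × 0.85 = 144.5, which matches 144 evaluable (72 per arm). Summing over all 2×2 tables that Fisher's test rejects, power at 65.5% vs 86.4% is 80.03%, and the difference detectable with 80% power is 20.89 points. The stated figure reproduces.

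**2. Effect of one covariate, by simulation.** Patient-level logistic regression, 72 per arm, one standard-normal covariate, intercepts set so that the marginal rates stay at 65.5% and 86.4%. There were 4,000 trials per row, with a Wald test of arm at |z| > 1.96. R² is the share of outcome variance explained.

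| Assumed log-odds per SD | R² control / Penny | Unadjusted power | Adjusted power | Gain (points) |
|---|---|---|---|---|
| 0 | 0 / 0 | 84.4% | 84.1% | −0.3 |
| 0.3 | 0.020 / 0.011 | 85.1% | 85.6% | 0.5 |
| 0.5 | 0.051 / 0.029 | 84.4% | 85.9% | 1.5 |
| 0.75 | 0.104 / 0.065 | 84.6% | 87.4% | 2.8 |
| 1.0 | 0.164 / 0.110 | 84.2% | 88.8% | 4.6 |
| 1.4 | 0.259 / 0.193 | 85.2% | 92.3% | 7.1 |

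With no arm effect (log-odds 0.75), type I error was 5.1% both ways. Each power figure has a standard error of about √(0.85 × 0.15 / 4000) = 0.0056, or 0.6 points, so gains under a point are close to nothing. The unadjusted level is about 84 to 85% rather than 80% because the logistic Wald test is less conservative than Fisher's test. Gains should be read within one scale.

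**3. Weak covariates and longer lists** (likelihood-ratio test):
- one covariate at 0.2: 84.7% to 85.0%; at 0.3: 86.7% to 86.9%;
- one true predictor at 0.5 in a four-covariate model: 84.8% to 85.7%, a gain of 0.9;
- three predictors at 0.2 each: 85.5% to 86.2%, a gain of 0.7;
- four covariates of pure noise: 85.8% to 85.4%, a loss of 0.4.

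**4. Cross-check on the Fisher scale.** Effective n per arm = 72 / (1 − R²), rounded and put back into the exact power:

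| R² | Effective n | SE multiplier √(1 − R²) | Power | Detectable difference |
|---|---|---|---|---|
| 0 | 72 | 1 | 80.0% | 20.9 |
| 0.02 | 73.5 | 0.990 | 80.5% | 20.8 |
| 0.05 | 75.8 | 0.975 | 82.6% | 20.4 |
| 0.10 | 80.0 | 0.949 | 84.8% | 19.9 |
| 0.20 | 90.0 | 0.894 | 88.9% | 18.9 |

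This method applies the same R² to both arms. In step 2 R² is smaller in the Penny arm, so these rows are on the generous side.

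**5. Room for covariates.** Expected non-adherent patients: 72 × 0.345 + 72 × 0.136 = 24.8 + 9.8 = 34.6, about 35.

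**Limit.** All of this uses the patient-level endpoint on which section 5.5 sizes the trial. The weekly repeated-measures model in 9.1 was not simulated, because its within-patient correlation is not given.

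**The case against.** The strongest reply is that this is a single-centre pilot with a valid unadjusted analysis that meets its stated power, and that the promised gain rests on assumed strengths. That stands. At 0.2 to 0.3 log-odds per SD there is essentially no gain.

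The second reply is that useful covariates may not have been collected. The documents do not place SEAMS, ESAS or the visual analogue adherence scale at T0, and the survey appendix is not in the available text. Section 9.2 treats symptom management and self-efficacy as intermediate outcomes and does not claim that their baseline scores predict MEMS adherence. A baseline value of the outcome itself cannot exist, because the caps arrive after the survey. This also stands, and it makes each named covariate conditional.

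A reader might go further in three ways that the documents do not support:
- **That baseline data go only into significance tests.** True within 9.1, but the Protocol Summary and 9.2 also assign them to mediator and moderator analyses. Those analyses do not sharpen the primary estimate.
- **That the trial is underpowered, or the 80% wrong.** The figure is for an unadjusted Fisher's test and reproduces. It does not depend on adjustment.
- **That chance imbalance invalidates the unadjusted result.** Randomisation and the confidence interval already allow for it; simulated type I error was 5.1% with and without adjustment.

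None of this removes the case for the change: even useless covariates cost almost nothing (step 3), and a pre-specified list settles in advance how imbalance is handled.

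**Conclusion.** The point holds as a missed efficiency and a gap in pre-specification, not as an error. The primary model uses no baseline survey or prognostic covariate, although the survey is complete for every randomised patient apart from skipped items.

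The size cannot be fixed from the documents. For one covariate on the patient-level endpoint, under assumed strengths, the power gain runs from about zero (0.2 to 0.3 log-odds per SD), through about 1 to 1.5 points (0.5) and about 3 to 5 points (0.75 to 1.0), to about 7 points (1.4). It rests on alpha of 0.05 two-sided, 72 evaluable per arm, the planned rates, and T0 carrying at least one prognostic score. Rating: cheap improvement.

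**What to change.** In section 9.1:

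1. Pre-specify two or three prognostic covariates measured at T0 and add them to the primary model, with medication status (new or prevalent start). Candidates are SEAMS self-efficacy, ESAS symptom burden and, for patients already on therapy, visual analogue adherence. Include each only after confirming that the T0 survey carries it. Set the adherence score to a constant for new starts, so that the medication status term absorbs the difference. State a rule for skipped items that does not use arm.
2. Replace the between-arm baseline tests with a descriptive table.
3. Report the arm effect as a standardised difference: predict each patient's probability of being adherent under Penny and under usual care, average each over all patients, and subtract. Give it in percentage points with a 95% CI. With a logit link, adjustment changes the odds ratio from marginal to conditional; the standardised difference avoids that. It should be computed on the patient-level 95% classification, so that it can be read against the 20.9-point design effect.

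The cost is SAP wording, settled before anyone analyses outcomes by arm. No new data, patients or visits are needed. The small downside is over-fitting: with about 35 non-adherent patients expected, the list should not grow beyond this.
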